11.4.2 Laboratory Data

The following routine clinical laboratory tests will be carried out throughout the study.

- Haematology: haemoglobin, haematocrit, white blood cells (WBC), neutrophils, lymphocytes, monocytes, eosinophils, basophils, platelet count, ESR
- Biochemistry: sodium, potassium, calcium, phosphate, glucose, blood urea nitrogen (BUN)
 /urea, creatinine, aspartate transaminase (AST), alanine transaminase (ALT), GLDH, lipase,
 alkaline phosphatase, gamma-glutamyl-transferase (GGT), total bilirubin, total protein, albumin,
 lactate dehydrogenase (LDH), CRP, T3, T4, TSH
- Stools: faecal calprotectin

The absolute values of each parameter and changes from baseline will be summarised at each visit (*Tables 14.3.2.1.1 to 14.3.2.1.3*). Laboratory parameters classified as normal/ abnormal non clinically significant (NCS)/ abnormal clinically significant (CS) will be presented in a shift table showing changes from baseline to each visit for patients with at least one abnormal CS value (*Tables 14.3.2.2.1 to 14.3.2.2.3*).

If laboratory results are repeated at the same visit, the repeated result will be used in summaries (instead of the original one) provided the sample was taken within the visit window, otherwise the original result will be used. All results will be listed.

Laboratory results at unscheduled visits will be included in the listings but will not be summarised.

Pregnancy data will be listed only.

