9.3. Safety Analyses

Adverse events will be coded using the standard dictionary (MedDRA) down to the lower level term (LLT).

An overall summary table will be presented (Any adverse event, any treatment emergent adverse event (TEAE), any serious adverse event (SAE), death, any grade 3 or higher adverse events from baseline to the end of Study. This analysis will be conducted on SAF population.

Two periods will be defined for TEAE:

- Any adverse event which occurs or worsens from first dosing to Day 56;
- Any adverse event which occurs after Day 56.

Adverse events will be described by primary system organ class and preferred term. Numbers and percentage of subjects, and number of occurrence of adverse event will be presented for:

- TEAE:
- Serious TEAE;
- TEAE leading to drug discontinuation;
- TEAE of grade 3 or 4;
- TEAE for which relationship with the study drug is recorded as possible or probable.

Analysis of safety will be performed on the safety data set consisting all subjects who received at least one dose of ABX464 in the study.

Primary safety endpoint, the rate of all treatment emergent adverse experiences will be compared between the study groups by stratified likelihood ratio chi-square test on a 10% one-sided significance level.

Further assessment of safety will be based on the frequency of adverse events (with and without regard to causality) graded according to the CTC-AE Classification and also, the review of individual values for clinical laboratory data, vital signs and ECG focusing on the detection of abnormal values and PCSAs [potentially clinically significant abnormalities (PCSAs) determined upon investigator considerations].

Adverse events will be tabulated (counts and percents) by group. All adverse events will be listed and the data will be tabulated by body system/organ class. Adverse event tabulations will include all treatment emergent adverse events, which will be further classified by severity, and relationship to treatment and dose level.

Clinical laboratory parameters, vital signs, ECG will be summarized by using descriptive statistics (n, mean, SD, SEM, median, minimum and maximum). Number of subjects with at least one abnormal values will be tabulated (counts and percents) for each parameter in summary shift tables, by group and dose.

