9.3.1. Clinical laboratory evaluation

Descriptive statistics for laboratory parameters will be computed at each scheduled assessment. If relevant for some parameter, change from baseline will also be tabulated.

In addition, shift tables from baseline will be presented.

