4.2.2 Other Secondary Endpoints

- The change from baseline in faecal calprotectin levels at Week 4 and Week 8 compared to placebo.
- The change from screening in TMS in subjects receiving ABX464 at Week 8 compared to placebo.
- The change from baseline in Partial Mayo Score (PMS) in subjects receiving ABX464 at Week 4 and Week 8 compared to placebo.
- The proportion of subjects achieving endoscopic remission at Week 8. Endoscopic remission is defined as a Mayo endoscopic sub-score of zero.
- The proportion of subjects achieving mucosal healing at Week 8. Mucosal healing is defined as a Mayo endoscopic sub-score of less than or equal to one.
- The proportion of subjects achieving a clinical response at Week 8. Clinical response is defined
 as the reduction of at least 3 points in TMS and 30% from baseline score with a decrease of at
 least 1 point in bleeding sub-score or an absolute bleeding sub-score of 0 or 1
- The scores and changes from baseline in mental health (MH) and physical health (PH) component summary measures of the SF-36 Questionnaire at Week 4 and Week 8.
- The number of incidences of TEAEs.
- The number of incidences of TEAEs of special interest.
- The number of incidences of TEAEs leading to investigational medicinal product (IMP) discontinuation.

• The number of incidences of specific laboratory abnormalities.

The following list includes all endpoints to be assessed by Abivax. The methods for their analysis are not included in this SAP:

- The change from screening in IL-22 expression levels in serum and rectal/sigmoidal tissue at Week 8 compared to placebo.
- The change from baseline in microRNA-124 levels in whole blood (PAXgene®) and in tissue (RNA later) at Week 4 and Week 8 compared to placebo.
- The change from screening in the histopathology/infiltrate (rectal/sigmoidal biopsies) assessed by the Geboes score at Week 8 compared to placebo.
- The change from screening in rectal microbiota using taxonomic markers at Week 8 compared to placebo.

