10 STATISTICAL METHODS

10.1 GENERAL PRINCIPLES

All statistical methods will be based on the International Conference on Harmonisation (ICH) E9 document "Statistical Principles for Clinical Trials".

Data will be summarised by treatment group. A total column showing all patients will be included for baseline and safety summaries. Where appropriate, data will also be summarised by visit with summaries for each visit attended as scheduled and an additional summary for final (last scheduled visit or early withdrawal). The format of the summaries is defined in the shells at the end of this document.

In summary and analysis tables of continuous variables, standard descriptive statistics (N, mean, standard deviation [SD], median, minimum and maximum) will be presented. Quartiles, least squares mean (LS mean), standard error (SE) and 95% confidence interval (CI) will be presented in the statistical analysis outputs as appropriate. For PK summaries, arithmetic mean (AM), geometric mean (GM) and coefficient of variation (%CV) will be used to summarise the data. The minimum and maximum statistics will be presented in summary tables to the same number of significant figures as the original data. The mean/AM, median, LS mean, GM, CI, SD and SE will be presented to one more significant than the original data.

For numeric data which includes non-numeric values (e.g. PK data reported as below limit of quantification [BLQ] or lab results reported as < 10 or > 100) the following principles will be applied when summarising the data:

- BLQ will be replaced with a value that is ½ of the lower limit of quantification (LLQ)
- Results reported as < x will be treated in the same way as BLQ with LLQ=x
- Otherwise AM, GM, SD, Cl and %CV will not be calculated
- Whenever meaningful, minimum, median and maximum will be presented based on the reported data (e.g. minimum = <10, median = 20, maximum = >100)

In summary tables of categorical variables, the number of non-missing observations by category will be presented with percentages. The number of missing observations will also be presented when non-zero. Unless otherwise specified, the denominator for each percentage will be the number of non-missing observations within the column. All percentages will be presented to one decimal place.

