11.4.4 Physical Examination

A physical examination will be conducted at all visits.

Physical examination data will be listed only.

11.4.5 12-Lead ECG

A 12-lead ECG will be completed at baseline, Day 28, Day 56 and EOS.

The number and percentage of the patients with Normal / Abnormal NCS / Abnormal CS ECG results will be summarised at each visit (*Table 14.3.4.1*). A shift table will be presented, for patients with at least one Abnormal CS value, showing changes from baseline to each visit (*Tables 14.3.4.2*).

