00	xx	xx (xx.x%)	××	xx (xx.x%)	xx	xx (xx.x%)
РΥ	××	xx (xx.x%)	xx	xx (xx.x%)	xx	xx (xx.x%)
PT	xx	xx (xx.x%)	xx	xx (xx.x%)	xx	xx (xx.x%)
Etc	xx	xx (xx.x%)	xx	xx (xx.x%)	××	xx (xx.x%)

The table presents number of events (n) and number and percentage of patients (N(%)) The denominator for each percentage is the number of patients within the column

Repeat for moderate and severe intensity on a new page.

Source: Listing 16.x.x

Path\Filename

Page x/y

This layout also applies to:
Table 14.3.1.3.7.2 Treatment-Emergent Adverse Events, by Intensity and SOC and PT: Period 2 (Safety Set)

Version date: 23 August 2018

Page 54 of 93

Table 14.3.2.1.1 Summary of Haematology Parameters (Safety Set)

ddMMMyyyy

		ABX-464	Placebo	Total
	***************************************	(N=xx)	(N=xx)	(N=xx)
Haematocrit				
Baseline	N	xx	xx	xx
	Mean	xx.xx	xx.xx	xx.xx
	SD	xx.xx	xx.xx	xx.xx
	Median	xx.xx	xx.xx	xx.xx
	Minimum	xx.x	xx.x	xx.x
	Maximum	xx.x	xx.x	xx.x
Day 7				
Etc				
Etc				
purce: Listing 16.x.x				
ath\Filename				Page x/y

Version date: 23 August 2018

This layout also applies to:

Page 55 of 93

Table 14.3.2.1.2 Summary of Biochemistry Parameters (Safety Set) Table 14.3.2.1.3 Summary of Stool Results (Safety Set)

Version date: 23 August 2018

Page 56 of 93

ddMMMyyyy

ABX464-101 Table 14.3.5.1 Shift Table of Haematology Parameters (Safety Set)

ABX-464 Placebo (N≃xx) (N=xx) (N=xx) Baseline Baseline Baseline Normal Normal Normal Abnormal NCS Abnormal NCS Abnormal NCS Abnormal CS Abnormal CS Abnormal CS Haematocrit Day 7 Normal xx (xx.x%) Abnormal NCS xx (xx.x%) Abnormal CS xx (xx.x%) Day 14 Etc Etc

Version date: 23 August 2018

Page 57 of 93

CS=Clinically Significant; NCS=Non Clinically Significant

The denominator for each percentage is the number of non-missing observations within the column Baseline is defined as the last non-missing value before the first dose of study drug.

Source: Listing 16.x.x

Path\Filename

Page x/y

This layout also applies to:
Table 14.3.2.2.2 Shift Table of Biochemistry Parameters (Safety Set)
Table 14.3.2.2.3 Shift Table of Stool Results (Safety Set)
Table 14.3.4.2 Shift Table of 12-Lead Electrocardiogram (Safety Set)

ABX464-101

Table 14.3.3 Vital Signs, including Weight (Safety Set)

ddMMMyyyy

		ABX-464	Placebo	Total
		(N=xx)	(N=xx)	(N≃xx)
Systolic BP (mmHg)				
Baseline	Ŋ	xx	xx	xx
	Mean	xx.xx	xx.xx	XX.XX
	SD	xx.xx	xx.xx	XX.XX
	Median	xx.xx	XX.XX	xx.xx
	Minimum	xx.x	xx.x	xx.x
	Maximum	xx.x	xx.x	xx.x
Day 7				
Etc				

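### The laboratory shift tables cover only patients who had a clinically significant value, so their percentages are not incidence by arm

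*SAP*

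**What the plan says.** - **Laboratory shift tables (SAP 11.4.2, Tables 14.3.2.2.1 to 14.3.2.2.3).** Results in the three categories "will be presented in a shift table showing changes from baseline to each visit for patients with at least one abnormal CS value".
- **Denominator (SAP section 15, haematology shift shell, also used for biochemistry, stool results and ECG).** "The denominator for each percentage is the number of non-missing observations within the column". SAP 10.1 has the same default: "the denominator for each percentage will be the number of non-missing observations within the column". No other denominator is given. The shell is titled Safety Set, shows an N for each arm, and splits each arm into columns by baseline category.
- **ECG (SAP 11.4.5).** The shift table carries the same limit: "A shift table will be presented, for patients with at least one Abnormal CS value, showing changes from baseline to each visit". Just before it, with no limit: "The number and percentage of the patients with Normal / Abnormal NCS / Abnormal CS ECG results will be summarised at each visit" (Table 14.3.4.1, Safety Set).
- **Protocol 9.3.** "Number of subjects with at least one abnormal values will be tabulated (counts and percents) for each parameter in summary shift tables", by group. Protocol 9.3.1 adds: "In addition, shift tables from baseline will be presented". Neither section restricts the tables to patients with a CS value.
- **Endpoint (SAP 4.2.2, also Protocol 2.4).** "The number of incidences of specific laboratory abnormalities" is a listed secondary endpoint.

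**The concern.** The filter selects patients on the outcome that the table is meant to describe. If the percentages are then taken among the selected patients, they say how often a patient who was CS at some time is CS at a given visit. They do not say what share of the arm became abnormal. Two arms with very different incidence can print similar percentages.

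A patient whose results move only from normal to NCS does not qualify, so even the raw count of such shifts is lost.

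Safety is the primary objective, and laboratory abnormalities are a listed endpoint. In the SAP's list of tables, the only other laboratory tables are continuous summaries (14.3.2.1.1 to 14.3.2.1.3). No laboratory table therefore gives n/N (%) abnormal by arm.

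**Working it through.** The plan attaches no figure to these tables, so there is none to reproduce, and its sample-size figures do not depend on this point. All event rates below are assumptions. The arm sizes, 20 and 10, come from SAP 3.1.

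**1. What the percentage estimates.** Let *a* be the number of patients in an arm of size *n* who are ever CS on a parameter, and *s* the share of them who are CS at a given visit. For simplicity, everyone selected has a normal baseline (so all fall in one column of the shell) and no value is missing.

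- Restricted table: *a·s / a = s*. The number of affected patients cancels.
- Whole arm: *a·s / n*.

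| Ever CS, ABX464 vs placebo | *s* (both arms) | Restricted table | Whole arm |
|---|---|---|---|
| 6/20 vs 1/10 | 1 | 100% vs 100% | 30% vs 10% |
| 8/20 vs 1/10 | 1 | 100% vs 100% | 40% vs 10% |
| 10/20 vs 1/10 | 1 | 100% vs 100% | 50% vs 10% |
| 10/20 vs 1/10 | 0.5 (expected values) | 50% vs 50% | 25% vs 5% |
| 12/20 vs 2/10 | 1 | 100% vs 100% | 60% vs 20% |

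**2. Relaxing equal recurrence.** The equal restricted percentages above follow from giving both arms the same *s*. Suppose instead that CS status is independent across the five post-baseline laboratory visits in the flow chart (Days 7, 14, 28, 56, 63), with risk *p* at each. The restricted percentage is then *p* / [1 − (1 − *p*)^5].

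- *p* = 50% vs 10%: 0.5/0.969 = 52% vs 0.1/0.410 = 24%. Ever CS is 97% vs 41%.
- *p* = 10% vs 2%: 0.1/0.410 = 24% vs 0.02/0.096 = 21%. Ever CS is 41% vs 10%.

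The true visit-level ratio is 5 in both cases. The restricted table shows a ratio of about 2.1 (0.516/0.244) in the first and about 1.2 (0.244/0.208) in the second. With three visits in place of five, the percentages are 57% vs 37% and 37% vs 34%.

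**3. Chance that no placebo patient enters the table.** With ever-CS risk *r* and 10 placebo patients, this is (1 − *r*)^10:

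- *r* = 2%: 0.98^10 = 82%
- *r* = 5%: 0.95^10 = 60%
- *r* = 10%: 0.90^10 = 35%

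The placebo percentage then has no denominator. These figures treat one parameter at a time. If a CS value on any parameter qualifies a patient, *r* is larger and the chance smaller. The SAP does not say which rule applies, or whether the qualifying value must come after baseline.

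**The case against.** The strongest case on the other side has five parts.

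- **The denominator is inferred.** The footnote is the SAP's generic one, the shell is titled Safety Set, and SAP section 15 says that table headings name the analysis set. This stands in part: the SAP nowhere states that it divides by the selected patients. But 11.4.2 does state which patients the table shows, and no other denominator is offered. If the header N is meant to be the full Safety Set, the SAP should say so.
- **Counts are printed.** The cells show counts beside percentages. With 8/20 against 1/10 ever CS, more ABX464 patients would be visible, and an empty placebo column beside a filled one is itself a contrast. This stands. A reader might infer that these tables cannot separate a toxic drug from placebo, but the documents do not support that: the counts remain, and step 2 shows the percentages can still differ (52% vs 24%). Nor does an arm with no CS patient vanish, because arms are columns; it only lacks a denominator.
- **Other outputs carry signal.** Under Protocol 8.3.1, laboratory findings judged CS are recorded as adverse events when they meet the definition, and the adverse event tables divide by all patients in the column. Laboratory values and changes are summarised by visit for the Safety Set, and all results are listed. This stands for CS findings. It does not replace a tabulation of NCS shifts, and means can hide a few outlying patients.
- **ECG is already covered.** A reader might extend the point in full to ECG. Table 14.3.4.1 gives unrestricted n (%) in each category by arm and visit, so that would be wrong.
- **The protocol also speaks of patients with at least one abnormal value.** It does, but as the quantity to be counted, not as a filter on who enters the table, and for any abnormal value, not only CS ones. The endpoint is worded as a number of incidences, yet Protocol 9.3 asks for percentages as well.

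**Conclusion.** The point holds for laboratory data. Followed as written, SAP 11.4.2 and the shell give percentages conditional on ever being CS, omit patients who shift only to NCS, and narrow Protocol 9.3 and 9.3.1 without explanation. No other laboratory table supplies n/N (%) abnormal by arm.

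The loss of contrast ranges from complete (equal recurrence in both arms) to partial (independent visits). Its size depends on assumed rates, while the cancellation in step 1 depends only on the denominator reading. The 60% and 35% figures for an empty placebo denominator assume ever-CS risks of 5% and 10% with 10 placebo patients.

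These tables are descriptive, no test rests on them, and the primary comparison of treatment-emergent adverse events is unaffected. For ECG only consistency is at issue.

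**What to change.** 1. In SAP 11.4.2, delete the clause that limits the shift tables to patients with a CS value. Delete the matching phrase in 11.4.5 for consistency.
2. In the shift-table shell, set the denominator to Safety Set patients in the arm who have both a baseline value and a value at that visit.
3. Add, for each laboratory parameter and arm, n/N (%) of Safety Set patients with at least one post-baseline abnormal value, as Protocol 9.3 plans, and with at least one post-baseline abnormal CS value. Removing the filter alone would not supply these counts, because a visit-by-visit shift table does not count patients who were ever abnormal.
4. Keep the CS-only view as a listing.

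The cost is two phrases of SAP text, one shell footnote and two added lines per laboratory parameter. The tables become longer. No new data are needed and the sample size is untouched.

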7.2. Premature trial discontinuation

A subject must be withdrawn at any time from the study for the following reasons:

Subject's premature trial discontinuation could occur for the following reasons:

- Investigator's decision;
- An Adverse Event or an intercurrent condition that preclude continuation of treatment;
 - o Specifically, an increase ≥ 2.0 x ULN in liver transaminases (AST/SGOT and/or ALT/SGPT), in Alkaline phosphatase or in total bilirubin should be considered a treatment discontinuation criterion
- Worsening of the UC defined as a 2-point increase from the screening MCS with 3 days of continuous rectal bleeding confirmed by flexible sigmoidoscopy with an endoscopy subscore of 2 points or higher;
- Major protocol violation;
- Subject's decision;
- · Withdrawal of consent;

A subject who prematurely exits the study for a non-drug related reason, will be replaced (i.e. an additional subject will be randomized and receive the next treatment allocation. This may or may not be the same treatment as the withdrawn subject).

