3.4 STUDY TIME POINTS

A screening visit will occur at Day -14, where procedures and laboratory tests are performed to determine eligibility of subjects. The Investigator will need to check the results of these procedures and if they are in line with the inclusion and exclusion criteria then the subject will be randomised. Note that the process of randomisation does not require a site visit by the subject.

At Day 0, study drug (ABX464 or its matching placebo) will be administered once a day at 50 mg for the next 56 days. Subjects will be seen at the site every week during the first month of treatment (Day 7, 14, 21 and 28) and then every two weeks during the second month (Day 42 and 56).

At Day 56, all subjects willing to carry on the study treatment will be able to take part in an open-label study (ABX464-102). In any other cases, the subjects will perform an EoS visit within a week after last dosing (Day 63). Subjects will be treated according to the standard of care since the last day of study treatment. The total duration of the study participation is 11 weeks.

Visits and visit windows will be as follows:

Visit	Day	Window
Screening	-14	± 3 days
Rand	lomisation	
Baseline/ First dose date	0	
	7	± 2 days
	14	± 2 days
Tuestus out a suis d	21	± 2 days
Treatment period	28	± 2 days
	42	± 4 days
	56	± 4 days
Enter follow-up study ABX464-1	02 or exit study an	d perform EoS visit
EoS	63	± 2 days

If more than one visit occurs within a window, the nearest to the scheduled time will be presented within the summaries.

See Section 16.1 for the Study Flow Chart.

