If changes in severity for the same TEAE have been reported separately but with the same adverse event (AE) number, they will be collapsed to a single AE with maximum severity for the summary tables, but listed as reported.

Classifications of medical history, concomitant medication and adverse events will be sorted alphabetically within the summary tables.

If any laboratory assessments are repeated at the same visit, the result from the repeat assessment will be used in summaries. Both values will be listed.

Data collected on the eCRF will be presented within data listings. The data listings will be sorted by treatment group, country, centre number, patient number and visit/week/day. Treatment group will be as allocated (randomised). If any patients receive the wrong treatment this will be flagged in all listings. Visits outside the visit windows will be identified within the listings.

The date format for all output presentations will be 'ddMMMyyyy'.

All statistical analysis will be performed using SAS 9.3 or higher.

P-values will be rounded to four decimal places. P-values less than 0.0001 will be reported as <0.0001 in tables.

If any of the assumptions underlying the formal statistical methods proposed are violated during the analysis of the final data, alternative statistical methods will be used and any changes documented in the statistical methods section of the CSR, including the rationale for use.

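### By-visit laboratory tables drop values superseded by a repeat and unscheduled results, and no planned table counts subjects with any abnormal value, as Protocol 9.3 requires

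*SAP*

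**What the plan says.** Four SAP rules decide which laboratory values reach the summaries.

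- **Repeats, SAP 11.4.2:** "the repeated result will be used in summaries (instead of the original one) provided the sample was taken within the visit window". Otherwise the original is used.
- **Repeats, SAP 10.1:** for a repeat at the same visit, "the result from the repeat assessment will be used in summaries". There is no window condition.
- **Unscheduled visits, SAP 11.4.2:** "Laboratory results at unscheduled visits will be included in the listings but will not be summarised".
- **More than one visit in a window, SAP 3.4:** "If more than one visit occurs within a window, the nearest to the scheduled time will be presented within the summaries".

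Nothing is deleted from the record. SAP 11.4.2 adds: "All results will be listed".

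The planned laboratory tables (14.3.2.1.x and 14.3.2.2.x) are by-visit descriptive statistics and a "shift table showing changes from baseline to each visit for patients with at least one abnormal CS value". Protocol 9.3 asks for something else: "Number of subjects with at least one abnormal values will be tabulated (counts and percents) for each parameter in summary shift tables". Protocol 2.4 and SAP 4.2.2 both name the incidence of specific laboratory abnormalities as a secondary endpoint, and neither says which abnormalities are meant. Protocol 7.2 sets a liver threshold, "an increase ≥ 2.0 x ULN in liver transaminases", which extends to alkaline phosphatase and total bilirubin.

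**The concern.** Laboratory safety tables should show whether any subject had an abnormal value at any time on treatment. These tables show one retained value per scheduled visit. A rise that has settled by the repeat, or that falls between scheduled laboratory visits, leaves the table cells.

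Safety is the primary objective and about 20 subjects receive ABX464, so one or two affected subjects can decide whether a finding is noticed when the arms are compared. The adverse event tables depend on the investigator calling the abnormality clinically significant. An objective laboratory table is the natural check on that judgement, and here it would miss the same cases.

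**Working it through.** **1. Trace four cases through the rules.**

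| Case | By-visit tables under SAP 11.4.2 | By-visit tables under SAP 10.1 |
|---|---|---|
| Abnormal original, normal in-window repeat | Normal shown | Normal shown |
| Abnormal original, normal repeat outside the window | Abnormal shown | Normal shown |
| Normal original, abnormal in-window repeat | Abnormal shown | Abnormal shown |
| Abnormal only at an unscheduled visit | Not shown | Not addressed |

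Rows 1 and 4 are the losses. Row 2 is where the two sections give different tables from the same data. Row 3 shows that the repeat rule is not one-directional.

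**2. Where unscheduled results would fall.** Protocol 5.1 and 5.2 schedule post-baseline haematology and biochemistry at D7, D14, D28, D56 and D63, and none between D28 and D56. With windows of ±2 days at D28 and ±4 days at D56, days 31 (28 + 2 + 1) to 51 (56 − 4 − 1), 21 days in all, lie outside every laboratory window. A sample taken then, other than at the D42 visit, belongs to an unscheduled visit and is not summarised. The SAP does not say how an extra sample taken at D42 would be handled.

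**3. Planned tables against the protocol.** None of the laboratory tables in SAP 14.1 or the shells gives a worst post-baseline value, a count of subjects with at least one abnormal value per parameter, or a count at 2.0 x ULN. The shift tables are confined to patients with a clinically significant value, so they cannot supply the Protocol 9.3 count, which covers any abnormal value. The SAP does not say whether a superseded or unscheduled value counts towards entry to the shift table. Even if it does, the by-visit cells show only the retained value.

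**4. The plan's own detection figures.** Protocol 9.4 and SAP 3.5 give 88% and 64% for seeing at least one event among 20 subjects at rates of 1:10 and 1:20. With P = 1 − (1 − p)^20:

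- p = 0.10: 1 − 0.90^20 = 87.8%
- p = 0.05: 1 − 0.95^20 = 64.2%

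Both reproduce.

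**5. The same metric with dropped samples.** Let f be the share of affected subjects whose abnormality appears only on a superseded or unscheduled sample. The documents give no value for f, so it is an assumption, shown as a range. The chance that at least one affected subject appears in the laboratory tables is P = 1 − (1 − p(1 − f))^20.

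| f (assumed) | p = 1:10 | p = 1:20 |
|---|---|---|
| 0 | 87.8% | 64.2% |
| 0.25 | 79.0% | 53.4% |
| 0.50 | 64.2% | 39.7% |
| 0.75 | 39.7% | 22.2% |

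At p = 1:10 the expected number of visible affected subjects is 20 × 0.10 × (1 − f), that is 2.0, 1.5, 1.0 and 0.5. A worst-value table built from all results corresponds to f = 0.

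**The case against.** The strongest reply is that little is hidden. Protocol 8.3.1 requires laboratory findings judged clinically significant to be recorded as adverse events, and those enter the by-arm TEAE tables. A liver rise that stops treatment can also appear in the tables of TEAEs leading to study drug discontinuation. SAP 10.1 adds a final summary that can take in early-withdrawal values. Protocol 9.3 relies on review of individual values, which is feasible with 30 subjects and complete listings. Using a repeat for one-value-per-visit statistics is an accepted convention. SAP 11.4.2 can be read as the specific rule that refines the general one in 10.1.

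Most of this stands, and it rules out two stronger readings.

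- **A reader might infer that transient abnormalities vanish from the safety tables.** They do not. The loss is confined to the laboratory tables, and only abnormalities judged not clinically significant can lack every by-arm display.
- **A reader might infer that the rules selectively strip out the highest values.** The documents give no reasons for repeats, and the rule can equally replace a normal value with an abnormal one. Later unscheduled follow-up of a scheduled abnormality leaves the scheduled value in place. A simulation can produce a dramatic loss: with baseline transaminase about 0.6 x ULN and a three-fold rise in 20% of subjects, half resolved on the log scale at the repeat, the share showing 2 x ULN or more falls from 8–10% to 1–1.5%. That requires every such value to be repeated in window. If a quarter to a half are repeated, roughly 5–8% remain. The larger drop is close to a worst case and should not be quoted as the effect.

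The reply does not answer the gap against Protocol 9.3. Listings are not a by-arm count, and the adverse event route depends on the judgement that the laboratory table should check.

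**Conclusion.** The point holds as a reporting gap in the laboratory tables. As written, the SAP yields by-arm laboratory tables that can miss an abnormality which improved on an in-window repeat or arose only at an unscheduled visit. An abnormality of that kind judged not clinically significant has no by-arm display at all. Separately, and whichever repeat rule is used, the tables do not deliver the Protocol 9.3 count of subjects with at least one abnormal value, which the specific laboratory abnormalities endpoint needs.

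The size cannot be fixed from the documents. Over assumed shares of 25% to 75%, the chance that a 1:10 abnormality shows in the laboratory tables is 79% to 40%, against 88% with nothing dropped. This takes the 20 subjects as independent, and the share is an assumption. The primary TEAE comparison is unaffected provided adverse events are recorded as the protocol requires.

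**What to change.** - Keep one value per visit for the by-visit descriptive statistics. Switching these to the original value is a matter of convention and is not needed.
- Reconcile the repeat rules in SAP 10.1 and 11.4.2, so that one rule governs a same-visit repeat taken outside the window.
- Add, by arm on the Safety Set, a shift table from baseline to worst post-baseline value for each parameter, using all post-baseline results: original, repeat and unscheduled.
- Add, by arm on the Safety Set and from the same results, the number and percentage of subjects with at least one abnormal value per parameter. Include any-time counts for AST, ALT, alkaline phosphatase and total bilirubin at the 2.0 x ULN threshold in Protocol 7.2.
- Define which specific laboratory abnormalities form the secondary endpoint.

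The cost is two tables from data already held and a few lines of SAP text. Sample size, power, alpha and trial conduct are unchanged.
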